5.3 Method of Treatment Assignment, Randomization and Blinding

Randomization and blinding are not applicable due to only one treatment group.

5.4 Baseline

Baseline value will be defined as the non-missing value before first treatment.

5.5 Change from Baseline

Value of change from baseline at any post baseline visit will be defined as the difference of the non-missing baseline value to the non-missing post baseline value i.e.

Change from baseline (Δ) = post-baseline value at visit X - baseline value, where both values are non-missing.

Percent change from baseline will be calculated as:

$(\text{Assessment value at post-baseline visit X} - \text{baseline value}) / \text{baseline value} * 100$.

5.6 End of treatment

This assessment will be performed at end of treatment or latest at week 12.

In this study Follow-up will be performed as an on-site visit if in accordance with routine clinical practice at Month 6.

The end of study is defined as the date of the last visit (or remote contact) of the last patient included in the study.

5.7 Treatment Start Day

Confidential and Proprietary to MEDA Pharma GmbH (A Viatris Company)

Statistical Analysis Plan

v 13.0 Annexure I

Page 14 of 21

Form Title: Statistical Analysis Plan

SOP Number: [REDACTED]	Current Version Number & Date: 1.0 & 30NOV2023	Previous Version Number & Document Date: 0.6 & 10NOV2023
---------------------------	---	--

Date of first Cystistat instillation date will be used for treatment start day i.e., Visit 2 (Week 1) in this study.

5.8 Treatment End Day

Date of last Cystistat instillation date will be used for treatment end day (i.e., Latest Week 12 (Month 3) or Additional Treatment Visit (After week 12 to Month 6) in this study). If the patient has not completed the study, then the last available non-missing date of Cystistat instillation will be used for treatment end day.

5.9 Duration of treatment exposure

Duration of treatment exposure is defined as the time the subjects will be on treatment during the study.

Duration of treatment exposure: number of days between the last instillation date and the first instillation date + 1 i.e., date of last instillation -date of first instillation +1.

5.10 Multiple Comparisons and Multiplicity

As this study is exploratory in character, no multiplicity adjustment will be performed for different endpoints.

5.11 Methods for Withdrawals, Missing Data

Subjects who are withdrawn prematurely from the study treatment will be included in all analyses (up to the date of withdrawal), regardless of the duration of treatment. The analysis will be done on observed data only, no imputation will be done for missing values.

5.12 Unscheduled visits and Early termination Visit.

As this is a real-life study, no fix visit schedule is foreseen. Therefore, also unscheduled visits are not applicable.

If the patient terminates early, withdraws or is withdrawn, the reason for early termination/withdrawal will be recorded.

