3.3 End of Study Definition

The end of study is defined as the date of the last visit (or remote contact) of the last patient included in the study.

Cystistat will be instilled into the bladder according to the instructions for use (13). The observation period for a patient in this study will end approximately 6 months after start of treatment (irrespective of the duration of treatment). If required, treatment will be continued thereafter under regular medical care.

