- If required, treatment with Cystistat will be continued thereafter under regular medical care. For all patients, a follow-up visit will be scheduled for approximately month 6.

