10 ADVERSE EVENTS AND INCIDENTS REPORTING

The adverse event collection period begins at signing of informed consent and incident collection period begins with the first administration of the investigational medical device. The collection time for adverse events and incidents continues until the end of the last study visit (or (e-)mail contact) of the patient. Adverse events and incidents occurring during this period need to be reported to the sponsor according to [Section 10.4.1 ‘Reporting of Adverse Events and Incidents’](#). The investigator is also responsible for notifying the sponsor if he/she becomes aware of any adverse event or incident after the study period has ended and it is considered related to the investigational medical device. Once an AE or incident is detected, it should be followed until its resolution or until it is judged by the principal investigator to be stable or permanent.

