The clinical course of each (related) adverse event should be followed until resolution or stabilization. Adverse events related to the investigational medical device that are still ongoing at the end of the study period must be followed up to determine the outcome. Any adverse event that occurs after the study period and is related to the investigational medical device or study participation should be recorded and communicated to the sponsor as per already described timelines in [Section 10.4.1](#).

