4.2 Study Initiation and Completion

The study duration for a patient will be approximately 6 months. The observation period for a patient in this study will end approximately 6 months after start of treatment (irrespective of the duration of treatment). If required, treatment will be continued thereafter under regular medical care.

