5.0 GENERAL CONSIDERATIONS FOR STATISTICAL ANALYSIS

All analysis will be based on CDISC compliant AdAM data (IG version: 1.1) derived from SDTM datasets (IG version 3.3).

The descriptive statistics for continuous variables will be presented with number (n) of non-missing observations, number of missing observations (nmiss), mean, standard deviation (SD), minimum, 5% percentile (P5), lower quartile (Q1), median, upper quartile (Q3), 95% percentile (P95) and maximum (range). For categorical data, number (n) and percentage of observations in the various categories of the endpoint will be presented, where percentage will be based on the total number of patients in the respective population or analysed subgroup if not stated otherwise. Individual patient data listings will also be provided. Depending on the study population, data compiled up to the point of discontinuation will be used for analysis. Subjects who are withdrawn prematurely from the study treatment will be included in all analyses (up to the date of withdrawal), regardless of the duration of treatment.

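### Read literally, SAP 5.0 and 5.11 end a patient's data when she is withdrawn from treatment, which conflicts with observation and analysis to month 6

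*SAP*

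**What the plan says.** SAP 5.11 gives the rule for early stoppers: "Subjects who are withdrawn prematurely from the study treatment will be included in all analyses (up to the date of withdrawal". The sentence then continues "regardless of the duration of treatment. The analysis will be done on observed data only", with no imputation of missing values. SAP 5.0 repeats the rule and puts another sentence before it: "Depending on the study population, data compiled up to the point of discontinuation will be used for analysis".

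The observation period is set elsewhere. SAP 4.2 states: "The observation period for a patient in this study will end approximately 6 months after start of treatment (irrespective of the duration of treatment". Protocol 3.3 agrees: "will end approximately 6 months after start of treatment (irrespective of the duration of treatment". Protocol 6.3 adds: "For all patients, a follow-up visit will be scheduled for approximately month 6". On safety, protocol 10 says: "The collection time for adverse events and incidents continues until the end of the last study visit". Protocol 10.2 requires that device-related adverse events "that are still ongoing at the end of the study period must be followed up to determine the outcome".

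The analysis sections follow that longer period. SAP 7.2 analyses BPIC-SS, VAS, voiding measures and PGA response at month 6, and presents flares and medication use until month 6. SAP 8.1 tabulates all adverse events and incidents, with outcome and date of resolution, and sets no on-treatment window.

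**The concern.** The only withdrawal named in the SAP 5.11 sentence is withdrawal from treatment. Taken at its word, a patient who stops Cystistat prematurely at week 4 and still attends at month 6 contributes nothing after she stops, although her data were collected. Her month-6 PGA, BPIC-SS, VAS and diary values would go, as would later adverse events, flares and medication use. So could the resolution of the event that made her stop.

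One programmer following 5.11 and another following 7.2 and 8.1 would build different month-6 and safety tables from the same SAP. Because the study is meant to confirm the benefit-risk balance, the safety tables matter most.

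**Working it through.** **The text**

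| Points to a cut at treatment stop | Points to data until study exit or month 6 |
|---|---|
| SAP 5.0 and 5.11 name withdrawal from treatment | The same sentence includes patients whatever their treatment duration |
| Protocol 10.3.5 uses *treatment withdrawn* for permanent discontinuation of treatment | Protocol 6 uses *discontinuation* for patients leaving the study |
| Protocol 4.2.3 and 6.5 separate stopping treatment from leaving the study, so naming treatment carries meaning | SAP 4.2 and protocol 3.3, 6.3 and 10 run to month 6 or the last study visit |
| | SAP 7.2 and 8.1 analyse month 6 and all adverse events and incidents |

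Nothing ranks 7.2 and 8.1 above 5.0 and 5.11, or the reverse. The cut date is also undefined. It could be the last instillation (recorded under protocol 7.1.8; treatment end day in SAP 5.8) or the closing assessment of protocol 6.5, which may come later.

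**Size, for illustration only**

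The point disputes no figure in the plan. The planned 74 includes 7 for dropout, which implies a base of 74 - 7 = 67. Then 67 x 1.1 = 73.7, or 74, and 67/0.9 = 74.4, or 75 when rounded up. The derivation of 67 is blacked out.

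Assumptions, none given in the documents:
- k = 1, 3 or 5 premature stoppers still attend month 6.
- All 74 patients are in the FAS, and stoppers stay in it.
- Pain VAS change is -25 mm in others and -5 mm in stoppers (a 20 mm gap, the same at the closing assessment and at month 6), with SD 25 mm.
- M = 74 or 60 patients have month-6 data.
- The correlation rho between the two time points is 0.4 to 0.8.

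1. *Observation lost per stopper*, taking month 6 as week 26: (26 - 4)/26 = 85% for a stop at week 4, and (26 - 8)/26 = 69% at week 8.
2. *Month-6 responder rate.* SAP 7.1 divides by the whole FAS and 7.2 carries that method to month 6, so an excluded PGA counts as non-response. The largest loss, if all k respond, is k/74: 1/74 = 1.4, 3/74 = 4.1 and 5/74 = 6.8 points. The smallest is 0. For scale, the 90% CI half-width at an assumed 60% rate is 1.645 x sqrt(0.6 x 0.4/74) = 9.4 points.
3. *Patients with an adverse event.* The maxima are again 1.4, 4.1 and 6.8 points too few, reached only if every stopper's only event falls after the cut. The loss is 0 if SAP 8.1 is followed as written.
4. *Month-6 pain VAS, descriptive mean.* The overstatement is 20 x k/M.
5. *Month-6 pain VAS, planned mixed model, closing assessments kept.* The overstatement is 20 x (1 - rho) x k/M. A simulation (3,000 runs per cell, 74 patients, 0 or 14 random dropouts after end of treatment) agreed within 0.04 mm.
6. *Same model, cut at the last instillation.* The closing values are lost too. The simulation gave the month-6 shifts in the last row, and end-of-treatment shifts of 0.26-0.27, 0.81-0.84 and 1.33-1.36 mm.

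| Month-6 overstatement (mm) | k = 1 | k = 3 | k = 5 |
|---|---|---|---|
| Descriptive, M = 74 | 0.27 | 0.81 | 1.35 |
| Descriptive, M = 60 | 0.33 | 1.00 | 1.67 |
| Mixed model, closing values kept | 0.05-0.20 | 0.16-0.60 | 0.27-1.00 |
| Mixed model, cut at last instillation | 0.27-0.31 | 0.80-0.93 | 1.33-1.53 |

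For scale, the 95% CI half-width is 1.99 x 25/sqrt(74) = 5.8 mm, or 6.4 mm with 60 patients.

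**The case against.** The strongest reply is that withdrawal from the study was meant. Several passages fit that:
- Protocol 4.2.3 lists an adverse event warranting treatment withdrawal among the reasons for not completing the study.
- Protocol 6 treats a patient who misses her next routine treatment and cannot be reached as withdrawn from the study.
- SAP 7.3 sets early termination against having data at the end-of-treatment visit.
- SAP 7.2 has its own term, premature termination of treatment, for stopping the device.
- The SAP 5.0 sentence on discontinuation is qualified by study population.

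The 5.11 sentence can also be read as an inclusion rule, since it does not say that later data are excluded. A programmer who simply follows 7.2 and 8.1 keeps everything, and a cut that discarded the closing assessments sought under protocol 6.5 would be odd.

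Much of this stands. The study-withdrawal reading is plausible, and premature stoppers who still attend month 6 may be few. Treatment duration is at the investigator's discretion, so a short planned course is not premature withdrawal. But the sentence names treatment, protocol 4.2.3 and 6.5 keep the two events apart, and no passage settles which is meant.

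A reader might infer more: that the SAP definitely discards off-treatment data, or that its month-6 results will be materially too favourable. The documents support neither. Exclusion follows only from the literal reading, and no passage says stoppers do worse. Nor should the 7 patients of the dropout allowance be used as k, giving 7/74 = 9.5 points. They are expected losses before end of treatment or week 12, not stoppers who remain under observation.

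**Conclusion.** The point holds as a conflict on the literal reading, not as a demonstrated bias. SAP 5.0 and 5.11 tie the cut to treatment withdrawal, while the observation rules and SAP 7.2 and 8.1 run to month 6 or cover all events. If study withdrawal was meant, the conflict disappears.

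The efficacy effects are small against sampling error on the assumed inputs. A lower responder rate would err on the conservative side. The primary PGA is largely protected provided the protocol 6.5 assessment is kept when it falls after the last instillation. All analyses are exploratory.

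The weightier consequence is for safety: a late event, or the outcome of an event that led to stopping, could be left out. That is reason enough to correct the text, and it should be fixed. Confidence is medium, because the intended meaning and the number of patients affected are unknown. The undefined cut date is a secondary point.

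**What to change.** Reword SAP 5.0 and 5.11 to say that all efficacy and safety data collected until withdrawal from the study (or of consent) or the month-6 visit are analysed, whether the patient is on or off treatment. State that this includes the early-termination assessment of protocol 6.5 when it is made after the last instillation. Use *withdrawal from the study* and *premature termination of treatment* as two separate terms throughout.

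If the analysis has already been run, state in the study report which rule was applied and how many patients it affected.

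The cost is a rewording of the affected sentences in two SAP sections. No new data are needed, because these assessments are already scheduled and entered in the eCRF, and no clinical rule changes.

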5.13 Analysis Software

All analysis will be performed using SAS® Software version 9.4 or later.

6.0 DEMOGRAPHICS AND OTHER BASELINE CHARACTERISTICS**6.1 Demographics**

Demographic variables and subject characteristics will be summarized descriptively. Demographic variables will include age, gender, and ethnicity.

6.2 Prior and Concomitant Medications

Form Title: Statistical Analysis Plan

SOP Number: [REDACTED]	Current Version Number & Date: 1.0 & 30NOV2023	Previous Version Number & Document Date: 0.6 & 10NOV2023
---------------------------	---	--

All prior and concomitant medications will be coded using World Health Organization Drug Dictionary (WHODDD), 1st March 2023 or later. The frequency and percent of prior and concomitant IC/BPS and pain medications will be tabulated by using Therapeutic class and Generic name for overall.

IC/BPS Medications: Medications entered with indication ‘Study indication (IC/BPS)’.

Pain Medications: Medications classified as “Drugs used in pain therapies“ based on WHODrug Standardised Drug Groupings (WHODrug SDGs), version 1st September 2023 or later.

Prior Medications: Medications started and stopped prior to enrolment into the study (i.e. start date and stop date at least one day before baseline visit).

Concomitant Medications: Medications started after enrolment into the study (i.e. start date on or after the day of baseline visit and stop date on or after day of baseline visit or ongoing).

Prior and Concomitant Medications: Medications started prior to enrolment into the study and continued during the study (i.e. start date at least one day before baseline visit and stop date on or after day of baseline visit or ongoing).

6.3 Baseline and Screening Conditions

6.3.1 Baseline Medical/Surgical History

Medical history will be coded using MedDRA dictionary version 26.0 or higher version. The frequency count (n) and percentage (%) of subjects will be summarized according to the coded terms of system organ class (SOC) and preferred term (PT) for Safety Population (SAF).

6.3.2 Baseline Physical Exam, vital sign and Laboratory assessment

Not Applicable

6.3.3 Measurement of Treatment Compliance

As measurement for compliance the total number of instillations (until end of treatment visit or latest week 12 and until Month 6) done as per instruction will be analysed by counts and percentages.

7.0 EFFICACY ANALYSES

The efficacy analyses will be performed on all the subjects in Full Analysis Set (FAS) if not stated otherwise.

7.1 Primary Efficacy Variable Analysis

The primary efficacy endpoint is the responder rate at the end of treatment or latest at week 12 as indicated by change on a seven-point Patient Global Assessment (PGA) scale where the patient is able to evaluate the overall change in her/his IC/BPS condition as markedly improved, moderately improved, slightly improved, no change, slightly worse, moderately worse or markedly worse. For the primary analysis, a responder is defined as a patient who had an improvement on the PGA scale (i.e. PGA evaluated as markedly improved, moderately

Form Title: Statistical Analysis Plan

SOP Number: [REDACTED]	Current Version Number & Date: 1.0 & 30NOV2023	Previous Version Number & Document Date: 0.6 & 10NOV2023
---------------------------	---	--

improved, or slightly improved. In case of slightly improved, patients will only be considered as responder if the question “Did therapy have a positive effect on your life and would you undergo this treatment again?” is answered with “Yes”).

PGA categories will be tabulated and responder rate will be calculated using total number of responders and dividing by total number of patients in FAS. The 90% confidence interval of rate will be estimated [REDACTED]

[REDACTED]

Additional Analysis of Primary Endpoint:

[REDACTED]

Additional sensitivity analyses may be performed to address for example the impact of missing data due to dropouts.

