8.3.3 Sensitivity Analysis of Primary Endpoint

8.3.4 Missing Data

Missing data will not be imputed. More details will be specified in the SAP.

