5.2.3 Full analysis set (FAS) population

All patients of the SAF who have at least one post baseline assessment of primary or secondary efficacy endpoint.

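### Does dividing PGA responders by all FAS patients conflict with the SAP's rule of no imputation?

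*SAP*

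**What the plan says.** SAP 7.1 sets the primary rate: "responder rate will be calculated using total number of responders and dividing by total number of patients in FAS", with a 90% confidence interval whose method is blacked out. The same section tabulates the PGA categories. SAP 7.2 gives the month-6 rate and the alternative responder definition the same analysis and reporting as the primary endpoint.

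Two general rules point the same way. SAP 5.0 describes categorical summaries by count and percentage, "where percentage will be based on the total number of patients in the respective population or analysed subgroup if not stated otherwise". SAP 7.0 adds: "The efficacy analyses will be performed on all the subjects in Full Analysis Set (FAS) if not stated otherwise".

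The FAS is defined in SAP 5.2.3 as "All patients of the SAF who have at least one post baseline assessment of primary or secondary efficacy endpoint". A PGA is not required; one diary entry after baseline is enough.

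On missing data, SAP 5.11 says "The analysis will be done on observed data only, no imputation will be done for missing values". Its preceding sentence says that prematurely withdrawn patients "will be included in all analyses (up to the date of withdrawal), regardless of the duration of treatment". Protocol 8.3.4 says: "Missing data will not be imputed. More details will be specified in the SAP".

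Three further provisions bear on the point. SAP 7.1 allows, but does not commit to, sensitivity analyses for dropout. SAP 7.3 plans an analysis of patients with end-of-treatment/week-12 data if more than 10 terminate early. Protocol 6.5 asks for a PGA at withdrawal.

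**The concern.** Put SAP 5.2.3 and 7.1 together and a FAS patient without a PGA is scored as a non-responder. Someone who has just read SAP 5.11 would expect a rate among patients who gave a PGA, and would get a different one without being told. The two could be mistaken for a contradiction that lets the analyst choose the denominator after seeing the data.

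The stake would be interpretation, above all at month 6. A patient with a PGA at week 12 but none at month 6 lowers the month-6 rate even if response among those assessed is unchanged, so attrition could be read as loss of effect. SAP 5.12 also does not say to which timepoint a PGA taken at withdrawal belongs.

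**Working it through.** **1. Is the denominator determined?**

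| Section | What it fixes |
|---|---|
| SAP 7.1 | Primary rate: responders over all FAS patients |
| SAP 5.0 | Default percentage base: the whole population |
| SAP 7.0 | Efficacy population: FAS |
| SAP 7.2 | Month-6 rates: same method as the primary |
| SAP 5.11, withdrawal sentence | Withdrawn patients stay in all analyses |
| SAP 5.11, last sentence | No value is filled in for a missing one |

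Only the last row could pull the other way. A fixed denominator supplies no PGA value: the category table still shows only the answers patients gave, and the rate is responders seen over patients in the set. The responder definition already works like this, since slight improvement counts only when the follow-up question is answered yes. The specific rule in 7.1 and the general rule in 5.11 can both be followed, and they yield one number.

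**2. The plan's own figure.** SAP 5.1 gives 74 patients, 7 of them added for about 10% dropout. The base is 74 − 7 = 67, and 67 × 1.10 = 73.7, which rounds up to 74. (Dividing instead, 67 / 0.90 = 74.4, gives 75.) The derivation of 67 is blacked out and cannot be checked.

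**3. Size of the gap.** Let p be the response rate among assessed patients and m the number of FAS patients without a PGA, with all 74 in the FAS. The FAS rate is p(74 − m)/74, so the gap is p × m/74. For p, I assume the 60 to 85% that both documents cite from earlier studies.

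- m = 1: 0.60/74 = 0.81 points to 0.85/74 = 1.15 points
- m = 3: 2.43 to 3.45 points
- m = 7: 5.68 to 8.04 points

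In whole patients, with exact binomial 90% intervals (an assumption, as the method is not visible):

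| No PGA | Among assessed | Over FAS | Gap (points) |
|---|---|---|---|
| 3 | 43/71 = 60.6% (50.1–70.3) | 43/74 = 58.1% (47.9–67.8) | 2.5 |
| 3 | 60/71 = 84.5% (75.7–91.1) | 60/74 = 81.1% (72.0–88.2) | 3.4 |
| 7 | 40/67 = 59.7% (48.9–69.8) | 40/74 = 54.1% (43.9–64.0) | 5.6 |
| 7 | 57/67 = 85.1% (76.0–91.7) | 57/74 = 77.0% (67.6–84.8) | 8.0 |

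Seven is an upper case at the planned dropout. It needs every dropout to have post-baseline data yet no PGA, although Protocol 6.5 seeks one at withdrawal. Dropouts with no post-baseline data leave the FAS altogether.

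**4. Month 6.** The documents give no figure for missing PGAs at month 6, so no total can be stated. The per-patient figure of 0.81 to 1.15 points carries over. Protocol 6.4 provides for remote collection, which should limit losses.

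**5. The withdrawal PGA.** The primary endpoint is taken at end of treatment, at the latest week 12, and the schedule places it on the last treatment day. For a patient who stops before week 12, the PGA from Protocol 6.5 is naturally her end-of-treatment value. What stays open is a withdrawal between week 12 and month 6. That cannot touch the primary rate where the week-12 PGA was taken. It moves the month-6 rate by at most 1/74 = 1.35 points for each such patient.

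**The case for a change.** The strongest case for acting is that the visible provisions do not guarantee a labelled rate among assessed patients. The SAP 7.3 analysis needs more than 10 early terminations. At 10% dropout in 74 patients the binomial probability of that is 0.118, so it would probably not run, and it covers end of treatment/week 12 only. With exactly 10 patients lacking a PGA, the most that leaves 7.3 untriggered if each is an early termination, the gap would be 8.0 points (38/64 = 59.4% against 38/74 = 51.4%) to 11.4 points (54/64 = 84.4% against 54/74 = 73.0%). The category tables allow the rate among assessed patients to be derived but do not print its interval. A declaration and one extra column per timepoint would cost little.

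The arithmetic stands, and so does the observation that no visible sentence states the non-response convention. The need for a change does not follow:

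- The counts behind the second rate will be in the category tables, and individual listings are planned (SAP 5.0). An interval follows from the counts.
- An analysis of this kind would belong exactly where the public copies are blank: after the interval sentence and under the additional primary analysis in SAP 7.1, and in Protocol 8.3.2 and 8.3.3. Because SAP 7.2 carries the primary method and reporting forward, that text could cover month 6 too. It cannot be called absent.
- The limit to data before withdrawal in SAP 5.11 does not reopen the month-6 denominator, which 7.2 settles by reference to 7.1.

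**Conclusion.** No change to the plan follows. The denominator is stated, consistent across the SAP and computable at both timepoints. It gives the lower of the two candidate rates, which is the cautious side for a single-arm study whose analyses the Protocol calls exploratory. Declaring the convention would leave the primary rate and its interval exactly as they are.

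The gap between the two rates is 0.8 to 1.1 points per missing PGA and 5.7 to 8.0 points in the seven-missing case. This assumes 74 patients in the FAS and 60 to 85% response among those assessed; the intervals shown also assume the exact binomial method. The month-6 gap cannot be totalled from the documents.

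What remains is a point of clarity that an analyst fills sensibly: SAP 5.11 does not refer to 7.1, and the SAP is silent on a PGA taken at withdrawal after week 12. A report that shows the number with a PGA beside the FAS rate lets readers separate attrition from non-response, and the planned tables already contain what is needed.
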